**LIST OF ABBREVIATIONS**

*Add all other abbreviations referenced in the protocol and delete any not referenced in the protocol.*

AE	adverse event
BUN	blood urea nitrogen
CFR	Code of Federal Regulations
CRF	case report form
DMC	Data Monitoring Committee
DSMB	Data Safety Monitoring Board
ESRD	End stage renal disease
FDA	Food and Drug Administration
GCP	Good Clinical Practice
HD	Hemodialysis
HIPAA	Health Insurance Portability and Accountability Act of 1996
ICF	informed consent form
IDH	intra-dialytic hypotension
IRB	Institutional Review Board
IV	intravenous
mEq	milliequivalent
PI	Principal Investigator
PHI	Protected Health Information
RAAS	renin-angiotensin-aldosterone system
SAE	serious adverse experience
SBP	systolic blood pressure

## PROTOCOL SYNOPSIS

TITLE	The BOLD Trial: B lood Pressure L owering in D ialysis Trial
PIs	[name], MSc [name], MAS
FUNDING ORGANIZATION	NIH-NIDDK and Satellite Healthcare
NUMBER OF SITES	2
RATIONALE	Treating home blood pressure may be better than treating dialysis unit blood pressure to improve outcomes in patients on maintenance hemodialysis
STUDY DESIGN	Randomized controlled trial
PRIMARY OBJECTIVE	
 
To determine the feasibility of and adherence to a strategy of dry weight adjustment and anti-hypertensive medication titration to achieve home systolic blood pressure <140 mmHg vs. a pre-dialysis systolic blood pressure <140 mmHg over 4 months.
 
To test the safety and tolerability of an intervention to achieve home systolic blood pressure <140 mmHg.
 

SECONDARY OBJECTIVES	
 
To determine acceptability of a Bluetooth-enable home blood pressure monitor in dialysis patients
 
To determine whether the strategy of targeting home systolic blood pressure versus in-center pre-dialysis systolic blood pressure leads to differences in blood pressure levels
 

NUMBER OF SUBJECTS	50 (or 25 in each of the two arms)
SUBJECT SELECTION CRITERIA	
Inclusion Criteria:
 
 
Provision of signed and dated informed consent form
 
Undergoing in-center, thrice weekly hemodialysis for treatment of end stage renal disease
 
Greater than 3 months since initiation of dialysis
 
Aged 18 years or above
 
Able to obtain a brachial blood pressure at dialysis and at home
 
 
Exclusion Criteria:
 
 
Pregnancy, anticipated pregnancy, or breastfeeding as this will require increase to more than three time a week dialysis and/or preclude use of some classes of blood pressure medications
 
Incarceration or institutionalized living which may prohibit measurement of home blood pressure
 
Participation in another intervention study that may affect blood
 

	
pressure
 
4. Patients in whom systolic blood pressure is not measurable (e.g. those with left ventricular assist devices)
 
5. Hypotension: average pre-dialysis systolic blood pressure <100 mmHg over last 2 weeks prior to screening while not taking any blood pressure medications
 
6. Life expectancy <4 months
 
7. Anticipated living donor kidney transplant within 4 months

INTERVENTION	
 
• Dry weight and anti-hypertensive medication adjustment to target home systolic blood pressure vs. in-center pre-dialysis systolic blood pressure <140 mmHg
 

DURATION OF SUBJECT PARTICIPATION AND DURATION OF STUDY	The total duration of the study is expected to be 24 months
PRIMARY ENDPOINT	
 
• Feasibility of intervention
 
• Adherence to intervention
 
• Safety
 
• Tolerability
 

SECONDARY ENDPOINTS	
 
• Of the home BP participants, we will determine the modality they choose to transmit their home BP readings
 
• Differences in blood pressures between treatment groups as assessed by blood pressure at dialysis and 44-hour intra-dialytic ambulatory blood pressure
 

STATISTICS Primary Analysis Plan	
 
• We will quantify the screen: enroll ratio
 
• We will report the proportion of participants in the home BP arm that complete the training, percent of home BP readings completed over the study period, and mean time from home BP measurement to transmission to the study team.
 
• We will quantify rates of completion and drop out in each treatment arm.
 
• We will report rates of hypotension and hypertension in each treatment arm.
 
• We will quantify rate of intra-dialytic hypotension and symptoms related to intra-dialytic hypotension in each treatment arm.
 

Rationale for Number of Subjects	This pilot study is designed to test study logistics and optimize study interventions within the confines of a pilot study budget, not to find statistically significant differences between the two arms.

## 1 INTRODUCTION

### 1.1 Background

Blood pressure (BP) is a powerful and modifiable risk factor for cardiovascular (CVD) events and death in the general population. Observational studies document a progressive increase in risk of BP-related end-organ damage as systolic BP (SBP) rises above 115 mmHg. Lowering of SBP to less than 140 mmHg had been the conventional target for treatment of hypertension. Recent data from the SPRINT trial showed that targeting even lower SBP targets (<120 mmHg) lowered rates of CVD events and death in an at-risk population with or without moderate maintenance kidney disease.

[figure not shown]
End-stage renal disease (ESRD) patients on maintenance maintenance hemodialysis (HD) have high rates of CVD events and death. Approximately 2 million ESRD patients worldwide are treated with HD. Reported CVD mortality rates are 10 to 30 times higher in HD patients compared with the general population. Hypertension is present in >90% of patients at the initiation of HD and persists over time in more than two-thirds. Improved management of BP in this high risk population could potentially yield substantial benefits.

Management of BP in HD patients is in dire need for better evidence to guide management. The management of BP in HD patients has long presented a conundrum for physicians. Differing from the general population, observational studies have repeatedly shown that HD patients with SBP measured prior to the dialysis treatment (pre-dialysis SBP; also referred to as dialysis-unit SBP) of <140 mmHg experience higher risk of mortality than those with SBP >140 mmHg (U-shaped association). And patients with pre-dialysis SBP of 150-179 mmHg appear to be at similar, if not lower, risk for death compared to those with pre-dialysis SBP of 140-149 mmHg, even accounting for differences in patient characteristics. Nevertheless, practice guidelines have continued to promote treating pre-dialysis SBP. For example, a pre-dialysis BP goal of <140/90 mmHg is recommended by Kidney Disease Outcomes Quality Initiative (KDOQI), despite the acknowledgement “it is unclear which blood pressure reading should be used as the guide for therapy.”

## 2 STUDY RATIONALE

[figure not shown]

We propose that solving this conundrum requires physicians to measure and treat out-of-dialysis-unit SBP rather than dialysis-unit SBP. We base our hypothesis on newly generated observational data from a NIH-sponsored multi-center cohort of incident HD patients (the Maintenance Renal Insufficiency Cohort [CRIC] study). We confirmed a “paradoxical” U-shaped association between *dialysis-unit SBP* and risk of all-cause mortality (**Figure 1 left panel**), but also showed a linear stepwise association between SBP *measured outside of the dialysis-unit* and risk of mortality (**Figure 1 right panel**), in a pattern similar to that in the general population.

Our data are consistent with prior single-center studies. We have since investigated adjudicated cardiovascular (CVD) events, which is novel as all-cause death is more commonly available as an outcome in dialysis epidemiology studies. Similar to all-cause mortality, there was a U-shaped association between dialysis-unit SBP and risk of CVD events (defined as a composite of heart failure, myocardial infarction, ischemic stroke, and peripheral artery disease events)(**Figure 2 left panel**). In contrast, there was a linear stepwise association between out-of-dialysis-unit SBP with risk of CVD events (**Figure 2 right panel**).

**Figure 2. Association of pre-dialysis SBP (left panel) and out-of-dialysis-unit SBP (right panel) and risk of cardiovascular events (Bansal...Hsu, *Hypertension* 2017)**

Since these associations were observed in the *same patients*, they refute prior hypotheses that the reason for the U-shaped association between dialysis unit SBP and adverse outcomes is due to inclusion of “sicker” patients (such as those with severe systolic heart failure) or due to physiological state unique to HD patients. Instead, we hypothesize the inability to mount an elevated BP in response to fluid accumulated between HD sessions—reflected in the dialysis-unit BP documented at the start of each HD session—is an adverse prognostic marker. In short, dialysis-unit BP may reflect mostly the transient effect of inter-dialytic volume expansion, rather than being a good overall indication of BP load as it relates to end-organ damage. Alternatively, perhaps some type of “white-coat hypertension/effect” particular to HD patient is operative here. But regardless of the exact pathophysiologic mechanism, these data strongly suggest that the focus should be on measuring and *treating out-of-dialysis-unit BP, rather than dialysis-unit BP*, which will be a significant change from current practice.

In our recent study, dialysis-unit SBP was generally higher than out-of-dialysis-unit SBP and the correlation was weak between the two measures (p=0.34). Nearly two-thirds (166/269=62%) of patients in this study with dialysis unit SBP >140 mmHg had out-of-

**Table 1. Cross-tabulation of dialysis-unit vs. out-of-dialysis-unit SBP in the CRIC study (N=377) (Bansal...Hsu, *Hypertension* 2017)**

dialysis-unit SBP <140 mmHg (**Table 1**). Thus, targeting dialysis-unit SBP may be leading to BP overtreatment in a substantial number of dialysis patients (those with high dialysis-unit but low out-of-dialysis-unit SBP), which may cause intra-dialytic hypotension, myocardial stunning and adverse cardiac remodeling. Concurrently, other patients may be undertreated (those with low dialysis-unit SBP but high out-of-dialysis-unit SBP), which may result in end-organ damage.

## 2.1 Risk / Benefit Assessment

This trial proposes to target an out-of-dialysis-unit SBP <140 mmHg vs. dialysis-unit SBP <140 mmHg among maintenance HD patients by adjusted estimated dry weight and anti-hypertensive medications. The algorithm will adjust RAAS inhibitors, beta-blockers, calcium channel blockers and other anti-hypertensive medications. The doses that will be prescribed will be within the scope of FDA approved doses. Potential risks of the study medications include: hypotension and bradycardia and associated symptoms such as dizziness. Subjects will be monitored for these potential risks closely through direct contact with the study coordinators. There is also a small potential risk of loss of confidentiality.

Blood pressure is one of the most important risk factors for cardiovascular disease and death in the general population. HD patients are at greatly increased risk of cardiovascular disease and death. So optimizing BP control in HD patients could potential yield substantial benefit. The proposed study is a pilot clinical trial test to test the feasibility and safety of treating dialysis-unit versus out-of-dialysis-unit blood pressure in dialysis patients. This will be most useful to practicing physicians, patients and public health planners.

Since the value of the findings is potentially large, we believe the proposed study's benefits outweigh the risks.

### **3 STUDY OBJECTIVES**

#### **3.1 Primary Objectives**

The primary objectives of the BOLD Trial are:

[figure not shown]
*To determine the feasibility of and adherence to a strategy of dry weight adjustment and anti-hypertensive medication titration to achieve home systolic blood pressure <140 mmHg vs. a pre-dialysis systolic blood pressure <140 mmHg over 4 months.*

*To test the safety and tolerability of an intervention to achieve home systolic blood pressure <140 mmHg.*

### **4 STUDY DESIGN**

#### **4.1 Study Overview**

This is a two center, placebo-controlled, randomized 4 month trial of 50 subjects. This will be a pilot clinical trial to test the feasibility, adherence, safety and tolerability of a strategy of targeting home SBP <140 mmHg vs. dialysis-unit (pre-dialysis) SBP <140 mmHg. These targets will be achieved using an algorithm of estimated dry weight and anti-hypertensive medication adjustment. Home BP measures will be recorded every other week and transmitted to the study team. We have chosen the same SBP target and the same algorithm for both arms so we can test the effect of the *setting* of BP measurement (rather than a specific BP target or medication). Participants will have contact with the study team every 2 weeks to obtain information on interim study outcomes (updated medical history, completion of study questionnaires) and adjust estimated dry weight and anti-hypertensive medications. A final study visit will occur at 4 months.

## 5 CRITERIA FOR EVALUATION

### 5.1 Primary Outcomes

#### Feasibility

- The study will determine how many eligible participants (and their nephrologists) agree to participate in the study (screen: enroll ratio)

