### 6.2 Inclusion Criteria

In order to be eligible to participate in this study, an individual must meet all of the following criteria:

1. Provision of signed and dated informed consent form
2. Undergoing in-center, thrice weekly hemodialysis for treatment of end stage renal disease
3. Greater than 3 months since initiation of dialysis
4. Aged 18 years or above
5. Able to obtain a brachial blood pressure at dialysis and at home

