## 6.4 Strategies for Recruitment and Retention

- Target study sample size: Our target sample size is 50 participants (25 participants at UCSF and 25 participants at UW).
- Source of participants: outpatient hemodialysis units affiliated with UCSF and UW or where UCSF and UW faculty practice.
- We will use the Electronic Medical Record (EMR) or directly query dialysis healthcare providers at UCSF and UW to identify eligible participants. We may confer with the primary nephrologist prior to approaching the patient if there are concerns about the suitability of the patient to participate in a research study.
- Incentives: Participants will be provided \$25-50 per month for participation in the study, depending on the visit number and the site.

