## 7 STUDY TREATMENTS

### 7.1 Method of Assigning Subjects to Treatment Groups

Enrolled subjects, stratified by site, will be randomly assigned in a 1:1 allocation to one of 2 groups (25 patients at both sites): (1) home SBP<140 mmHg and (2) in-center pre-dialysis SBP<140 mmHg. Randomization will be in done via Redcap in random size blocks to minimize bias in randomization and to ensure balanced assignment at each site. Both groups will be followed in parallel.

Prior to conducting any study-related activities, written informed consent and the Health Insurance Portability and Accountability Act (HIPAA) authorization must be signed and dated by the subject or subject's legal representative. If appropriate, assent must also be obtained prior to conducting any study-related activities.

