## 9 EVALUATIONS BY VISIT

### 9.1 Visit 0: Screening visit

1. Review the study with the subject and obtain written informed consent and HIPAA authorization
2. Assign the subject a unique screening number.
3. Record demographics data.

4. Record medical history, including a history of ESRD, dialysis access, dialysis initiation date and history of prior kidney transplants through participant questionnaires and review of the medical record
5. Record concomitant medications through participant questionnaires and review of the medical record
6. Record and review previous pre-dialysis blood pressures from the prior 2 weeks
7. Record previous clinical laboratory values (with corresponding date) taken from the dialysis and other medical records
8. Administer questionnaire of symptoms of hypotension during the last hemodialysis session(s): cramping (yes/no), dizziness/lightheadedness (yes/no), and fatigue (yes/no).
9. Ask open-ended question: "How long did it take you to recover from your last dialysis session" (responses in minutes or hours)
10. Obtain blood (5 ml) for serum pregnancy test for women of childbearing potential.

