### **14.3 Analysis of Primary Endpoint**

We will quantify the screen: enroll ratio. We will quantify rates of retention and adherence in each arm of the study and report characteristics of those lost to follow-up.

We will quantify % of patients in the home BP arm who can successfully complete home BP training, % who can transmit every other week home BP readings in a timely manner to the study team via any method and % who successfully implement electronic transfer of data via Bluetooth/smartphone.

Adverse events will be tabulated by treatment group and will include the number of patients for whom the event occurred, the rate of occurrence, and the severity and relationship to study intervention.

We will determine frequency of excessively high or low blood pressures, frequency of intra-dialytic hypotension and symptoms related to these in all enrollees.

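### Does reporting only a screen:enroll ratio leave the feasibility outcome of section 5.1 unanswered?

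*Combined protocol and SAP*

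**What the plan says.** Feasibility is the first primary outcome in section 5.1 and has one item: "The study will determine how many eligible participants (and their nephrologists) agree to participate in the study (screen: enroll ratio". The statistics part of the synopsis reduces this to "We will quantify the screen: enroll ratio". Section 14.3 does the same before turning to retention and adherence: "We will quantify the screen: enroll ratio. We will quantify rates of retention and adherence in each arm of the study".

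Four other places bear on the terms:

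- **Section 6.2** opens with "In order to be eligible to participate in this study, an individual must meet all of the following criteria", and its first criterion is "Provision of signed and dated informed consent form".
- **Section 6.4** describes recruitment: "We will use the Electronic Medical Record (EMR) or directly query dialysis healthcare providers at UCSF and UW to identify eligible participants". It adds that the team can speak to the patient's nephrologist beforehand if it doubts that the patient is suitable.
- **Section 9.1** begins the screening visit with "Review the study with the subject and obtain written informed consent and HIPAA authorization". The screening number is assigned in the next step.
- **Section 7.1** refers to people who are enrolled but still to be allocated: "Enrolled subjects, stratified by site, will be randomly assigned in a 1:1 allocation to one of 2 groups". Section 14.1 takes everyone randomised as the analysis set.

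Section 14 promises a detailed SAP before the final data are analysed. Section 14.5 gives the target of 50 as a budget figure for a pilot of logistics, with no power calculation.

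**The concern.** The outcome names two agreement counts, one for patients and one for nephrologists, while the planned analysis names a single ratio without a stated numerator or denominator. A screen-to-enrol ratio in general use can mix patients who refuse with patients who do not qualify. If this one did, it could not be read as an acceptance rate.

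The protocol's terms also pull in different directions. Signed consent is an eligibility criterion in section 6.2, so on a literal reading nobody eligible has refused. Screening numbers are issued after consent in section 9.1, so a ratio built on them would leave out everyone who declined. Nephrologist agreement is absent from section 14.3, the visit lists in section 9 and Appendix 1.

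At stake is one descriptive figure from a pilot. Recruitment acceptance is something a larger trial would want to know, and two sites using different denominators would blur it.

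**Working it through.** The documents give no value, target or formula for the ratio, so there is no figure to reproduce. The check is what the ratio would tell a reader under each reading of its terms.

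**Inputs.** E = 50 enrolled (section 14.5). S = number screened and n = number eligible among them; neither is given. The values of S below are assumptions for illustration. As a simplification, nobody is lost between consent and randomisation, so enrolled equals agreed. Write k = S/E.

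**Reading A: screened includes ineligible patients.** Agreement among eligible patients is E/n with E ≤ n ≤ S, so it lies between E/S = 1/k and 100%.

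| S | k | Lowest agreement (n = S) | Highest agreement (n = 50) |
|---|---|---|---|
| 100 | 2 | 50/100 = 50% | 50/50 = 100% |
| 150 | 3 | 50/150 = 33% | 50/50 = 100% |
| 200 | 4 | 50/200 = 25% | 50/50 = 100% |

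At S = 200 the number of refusals, n − E, runs from 200 − 50 = 150 down to 50 − 50 = 0. On this reading the ratio alone does not fix the patient figure.

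**Reading B: screened means eligible patients identified before approach.** Then S = n and agreement is exactly E/S = 1/k: 50% at 2:1, 33% at 3:1, 25% at 4:1. The ratio and the acceptance rate carry the same information.

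**Reading C: eligible taken literally from section 6.2.** Signed consent is a condition for being counted, so agreement is n/n = 100% whatever happens in recruitment.

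**Reading D: screened means holding a screening number.** Everyone counted has already consented, so the ratio describes only loss after consent.

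**Which reading fits the text.** C and D make the section 5.1 outcome empty, because a count of who agrees needs people who could have said no. A is possible but brings in ineligible patients, whom section 5.1 does not mention. B takes section 5.1 as written, with the ratio in brackets naming the count of eligible patients who agree. It also matches section 6.4, where eligible patients are found from records or providers before any approach. Consent as a criterion in section 6.2 governs who may take part; it is not a definition for counting recruitment.

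**Nephrologists.** Let i be the ineligible share and a the share of eligible patients whose nephrologist agrees. Patient agreement among those approached is E/(S(1 − i)a). With S = 200 and i = 50% (assumed), S(1 − i) = 100:

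- a = 100%: 50/100 = 50.0%
- a = 80%: 50/80 = 62.5%
- a = 60%: 50/60 = 83.3%

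The ratio is 4:1 in all three cases, so it cannot separate a nephrologist's refusal from a patient's. It does give the joint result, 50/100 = 50.0% of eligible patients, once the number eligible is known. Section 5.1 can be read as asking for that joint result, since it names patients and their nephrologists together.

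**The case for a change.** The strongest case for a change is about timing. Feasibility is a primary outcome, and a pilot of logistics exists largely to produce such figures. The SAP is due only before final analysis, and refusals that nobody logged during recruitment may not be recoverable by then. A patient held back after a talk with the nephrologist is neither ineligible nor a refuser, and no category is provided. Section 11.2 replaces subjects who withdraw within the first month, and nothing says whether the replaced ones count as enrolled.

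Part of this stands. No section defines the two terms for this ratio, the nephrologist item is not carried into section 14.3, and the log does have to be kept while recruitment runs.

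It does not amount to a defect in the design. Section 5.1 already commits the team to counting who agrees, and that cannot be done without recording approaches and refusals. The silence of section 9 and Appendix 1 is weak evidence that no log will exist: they list procedures for individual participants, beginning with consent, and a recruitment log sits outside such a schedule. That the sites would use different denominators is conjecture. A nephrologist tally would cover only a selected group, because section 6.4 makes the conversation optional.

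Fixing the ratio's wording would not settle everything either. If the denominator were eligible patients approached and enrolled meant randomised, a patient who consents and then fails a check made after consent, such as the pregnancy test at the screening visit, would again be mixed with those who refused. Separate counts make the figure readable, whatever the definition of the ratio.

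**Conclusion.** No change to the plan is needed. This is a gap in reporting detail that a sensible analyst would fill: show, by site, the numbers of eligible patients approached, declined, consented, found ineligible after consent and randomised, and note nephrologist refusals where one was consulted. Those counts follow from what section 5.1 already asks for, and the promised SAP can hold the definitions.

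Under the reading that best fits sections 5.1 and 6.4, the ratio gives patient acceptance directly as 1/k. The range from 1/k to 100% arises only if ineligible patients are counted as screened, which no section says, and its k values are illustrations. Nephrologist agreement as a separate figure remains unreported, but no estimate, comparison, threshold or safety rule in the plan depends on it.

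The conclusion rests on two assumptions: that the sites keep an ordinary recruitment log from the start, and that eligible in section 5.1 means eligible before consent. If no log were kept, refusals could be lost, and the damage would be confined to one descriptive feasibility figure.
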